8.7.5 Physical examinations

A full physical examination will be conducted at Screening and EOS as indicated in the Schedule of Assessments and will include a review of the following systems: head/neck/thyroid; eyes/ears/nose/throat (EENT); respiratory; cardiovascular; chest, lymph nodes; abdomen; skin; musculoskeletal; and neurological. Breast, anorectal, and genital examinations will be performed when medically indicated.

Physical examination data will be provided in data listings.

8.7.6 Electrocardiograms (ECG)

12-lead ECG measurements include (Heart Rate (bpm), QRS Duration (msec), PR Interval (msec), QT Interval (msec) and QTcF (msec)) and will be summarized using an 8-number summary by visit and treatment for all safety subjects for observed values and changes from Baseline. The overall ECG interpretation (Normal, Abnormal Not Clinically Significant, Abnormal Clinically Significant) will be summarized by presenting the number and percentage of subjects for each treatment group and time-point. In addition,

the number and percentage of subjects with significant changes in ECG parameters will be summarized by treatment. Change from Baseline in QTcF > 60 msec or a QTcF interval > 500 msec and QTcF > 450 msec for males and 470 msec for females at either screening or Baseline are considered as significant changes in ECG parameters.

Baseline is defined as the last value collected prior to first dose of study drug.

No statistical testing will be performed.

A by-subject listing will be provided.

8.8 Pharmacokinetics (PK) and Pharmacokinetics/Pharmacodynamics (PK/PD) Analysis

During the study, PK samples and PD samples for FGF19, C4, bile acid, and ALT will be collected according to one of two schedules on Days 1 and 84. Subjects agreeing to participate in the PK/PD substudy will have samples collected at four discrete times: predose and 2, 6, and 8 hours after administration of EDP-305 on Days 1 and 84. This scheme will be referred to as “intensive” sampling in this SAP. On Days 1 and 84, all other subjects will have a sample collected predose, a second sample collected 1 to 3 hours after administration of EDP-305, and a third sample collected at least 1 hour after the second sample. This scheme will be referred to as “sparse” sampling. Additionally, all subjects will have PK, FGF19, C4, bile acid, and ALT samples collected according to the sparse scheme on Weeks 2, 4, and 8.

For the sparse sampling scheme, the nominal window for the first post-dose sample is defined relative to the time of EDP-305 administration while the nominal window for the second post-dose sample is defined relative to the time of collection of the first post-dose sample. As a consequence, actual sampling times for the second post-dose sample may fall within the 1- to 3-hour window described for the first post-dose sample. For example, if the first post-dose sample is collected 1 hour after EDP-305 administration and the second post-dose sample is collected 1 hour later, then the both samples would fall within the 1- to 3-hour window. In addition, actual sampling times relative to EDP-305 administration for post-dose samples collected according to the sparse scheme may vary between subjects and study visits. To permit more meaningful summarization, post-dose samples collected according to the sparse scheme will be binned by actual elapsed time since the time of the reference dose of EDP-305 for each visit. Bins for sparse post-dose samples are described in Table 3. Bins may be modified based on the distribution of the data.

Table 3: Bin Time for Post-Dose Sparse Samples

Bin Time Midpoint (hr)	Range for actual post-dose sample time (relative to time of EDP-305 dose)
0.5	0 to < 1 h
2.0	≥ 1 to < 3 h

4.0	≥ 3 to < 5 h
6.0	≥ 5 to < 7 h
8.0	≥ 7 to < 9 h

For plotting purposes, sparse predose samples collected prior to administration of the reference dose of EDP-305 at each study visit will be assigned to a 0-hour bin. In the event that a predose sample is collected after administration of the reference dose of EDP-305 at a particular study visit, this sample will be assigned to a bin in the same manner as described above for sparse post-dose samples.

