9. Height to be assessed at Screening only
10. Full physical exam (PE) at screening and EOS Visit; subsequent PE should be targeted to review new signs and symptoms
11. Vital Signs include heart rate, respiratory rate, blood pressure, and will be measured once in the morning before the morning dose of study drug
12. Safety laboratory tests include chemistry (including liver function tests), hematology, and urinalysis and should be collected predose at all visits; See [Table 15](#) for details. Creatinine clearance will be calculated based on serum creatinine value performed all visits.. HbA1c will be obtained at Screening, Baseline, and Week 12 only
13. Lipids and CV risk markers to be collected are detailed in [Table 15](#)
14. Markers of inflammation include fibrinogen, CRP, IL6, IL1 β , TNF- α , TNF- β , alpha2 macroglobulin and haptoglobin (See [Table 15](#))
15. Samples will be collected from all subjects predose. Additional samples may be collected to further assess safety events.
16. Samples should be collected after a minimum 8 hr fast and before the subject takes the daily dose of study drug. All samples collected Day 1, Weeks 2, 4, 8 and 12 at predose and two samples postdose; with the first sample collected 1 to 3 hours postdose and the second sample collected at least 1 hour later
17. Collect PK/PD samples after a minimum 8 hr fast and before the daily dose of study drug. PK/PD samples on Days 1 and 84 (Week12) collected predose and 2, 6, and 8 hr postdose; Weeks 2, 4 and 8 at predose and two samples postdose with the first sample collected 1 to 3 hours postdose and the second sample collected at least 1 hr later
18. PK predose samples should be collected after a minimum 8 hour fast before the daily dose of study drug. PK samples collected Day 1, Weeks 2, 4, 8 and 12 at predose and two samples postdose; the first sample collected 1 to 3 hours postdose and the second sample at least 1 hour later. For subjects with persistent transaminase or ALP elevations, and have evidence of liver injury and who remain on study drug, [REDACTED].
19. Study drug given in the clinic on days where subject is seen in the clinic

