3.2 Randomization and blinding

3.2.1 Randomization

Subjects will be randomized to study treatment using an Interactive Web Response System (IWRS). Subjects will be stratified initially by prior liver biopsy vs no prior liver biopsy. Subjects will be randomized to the treatment groups shown below:

- Treatment Group 1 (N=50); EDP-305 1 mg orally for 12 weeks
- Treatment Group 2 (N=50); EDP-305 2.5 mg orally for 12 weeks

- Treatment Group 3 (N=25); Placebo (PBO) orally for 12 weeks

A minimum of 10 subjects per treatment group will be included in the PK/PD substudy. The randomization code will be produced by Enanta (or designee). The Enanta unblinded biostatistician or designee will review and approve the final randomization list.

During the Screening period, subjects will be identified by a unique screening number assigned by the clinical site. Subjects who have completed screening assessments and are eligible for participation in the study will be randomized before the first dose of study drug (Day -1 or Day 1) and assigned a unique subject number which will be used to identify the subject throughout the study.

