8.8.1.1 Analysis of Sparse PK Samples

The concentration data for EDP-305 and each metabolite collected according to the sparse sampling scheme will be summarized by active treatment arm, visit, and bin time midpoint. Concentrations that are below the limit of quantitation (BLQ) will be treated as zero for the computation of descriptive statistics. If more than 50% of subjects have postdose concentration values below BLQ, descriptive statistics will not be presented except for maximum and BLQ will be displayed for mean and minimum. The number of observations, arithmetic mean, standard deviation (SD), % coefficient of variation (%CV), median, minimum, maximum, geometric mean, and %CV of the geometric mean (%GCV) will be displayed. Linear and semi-log plots of the arithmetic mean concentration versus bin time will be created. The linear plots of mean concentrations will include the SD (\pm) for each mean. Composite (i.e. “spaghetti”) plots of individual subject EDP-305 and metabolite plasma concentrations versus time data will be created on both the linear and semi-logarithmic scales. A summary plot of the means and SD of the pre-dose concentrations at each visit will be provided by treatment.

Individual data will be presented in listing.

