8.8.1.2 Analysis of Intensive PK samples

The concentration data for EDP-305 and each metabolite collected according to the intensive sampling scheme will be summarized by active treatment arm, visit and nominal time since the reference dose. Concentrations that are BLQ will be treated as zero for the computation of descriptive statistics. If more than 50% of subjects have postdose concentration values below BLQ, descriptive statistics will not be presented except for maximum and BLQ will be displayed for mean and minimum. The number of observations, arithmetic mean, SD, %CV, median, minimum, maximum, geometric mean, and %GCV values will be displayed. Linear and semi-log plots of the arithmetic mean concentration versus nominal sampling time will be created. The linear plots of mean

concentrations will include the SD (\pm) for each mean. Composite (i.e. “spaghetti”) plots of individual subject EDP-305 and metabolite plasma concentrations versus time will be created on both the linear and semi-logarithmic scales. Predose samples collected under to the intensive sampling scheme will be pooled with those collected under the sparse sampling scheme for the purpose of creating the longitudinal summary plot of the means and standard deviations of the pre-dose concentrations (See Section 8.8.1.1). Linear and semi-logarithmic plots of the individual plasma concentration by actual sampling time will be provided by subject (one subject per page, Day 1 and Day 84 on same plot).

The PK parameters listed in Table 6 will be calculated as indicated for plasma EDP-305 and its metabolites, as applicable. PK parameters will be calculated by noncompartmental methods (only on Day 1 and Day 84).

Table 6: PK/PD Parameters for Subjects with Intensive Samples

PK Parameter	Description
AUC_{last}	The area under the plasma concentration-time curve from time zero to the time of the last quantifiable concentration computed using the linear up/log down trapezoidal rule.
C_{max}	Maximum observed concentration.
T_{last}	Time to last quantifiable concentration.
T_{max}	Time to reach C_{max} . If the maximum value occurs at more than one timepoint, T_{max} is defined as the first time point with this value.

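### Substudy subjects are outside the sparse PK and PD summaries on Day 1 and Week 12, so no planned Week 12 FGF19, C4 or bile acid ANCOVA uses the full efficacy population

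*SAP*

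**What the plan says.** SAP 8.8 describes two sampling schemes. Samples for PK, FGF19, C4, bile acid and ALT "will be collected according to one of two schedules on Days 1 and 84". The intensive scheme is for volunteers: "Subjects agreeing to participate in the PK/PD substudy will have samples collected at four discrete times: predose and 2, 6, and 8 hours". The sparse scheme is for the rest: "On Days 1 and 84, all other subjects will have a sample collected predose", then one at 1 to 3 h and another at least an hour after that. At the middle visits there is one scheme: "all subjects will have PK, FGF19, C4, bile acid, and ALT samples collected according to the sparse scheme on Weeks 2, 4, and 8". Protocol Table 19, footnote 17, gives the same timing for substudy subjects: "Weeks 2, 4 and 8 at predose and two samples postdose with the first sample collected 1 to 3 hours postdose".

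The summaries follow the scheme. In SAP 8.8.1.1, concentrations "collected according to the sparse sampling scheme will be summarized by active treatment arm, visit, and bin time midpoint". SAP 8.8.2.1 treats FGF19, C4 and bile acid in the same way and adds an ANCOVA for each bin at each visit, with most weight on Week 12. Intensive samples are reported apart, by nominal time, in SAP 8.8.1.2 and 8.8.2.2. There is one exception: intensive predose PK samples "will be pooled with those collected under the sparse sampling scheme for the purpose of creating the longitudinal summary plot".

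On size, SAP 3.2.1 says: "A minimum of 10 subjects per treatment group will be included in the PK/PD substudy". The planned arms are 50, 50 and 25, and no upper limit on the substudy is given. SAP 8.8.2 and Protocol 11.6.1 both name the efficacy population for the PD analysis.

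**The concern.** Substudy subjects are in the sparse tables at Weeks 2, 4 and 8 and out of them on Day 1 and Week 12. Two things follow.

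- **Reading across visits.** A step from Day 1 to Week 2, or from Week 8 to Week 12, can partly reflect who is in the table and not time on drug.
- **The Week 12 PD comparison.** FGF19, C4 and bile acid at Week 12 are listed as a secondary endpoint (SAP 4.2), yet their analysis is split into two models on separate subsets, one sparse and one intensive. SAP 8.6.3 holds no other model for them. SAP 8.8.2.4 does take in all subjects, but only with plots. The loss falls hardest on placebo, the smallest arm.

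**Working it through.** The documents give no figure of their own on this point, so there is nothing to reproduce first.

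**Inputs.** Planned arms 50/50/25 and at least 10 substudy subjects per arm (SAP 3.2.1); schemes and bin limits (SAP 8.8); a PK draw window of ±10 minutes (Protocol 8.4.3). The size of any difference between volunteers and others is an assumption, taken as 0.2 to 0.5 SD.

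**1. Who is in the sparse summaries**

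| Visit | Substudy subjects | Others | Largest sparse set (1 mg / 2.5 mg / placebo) |
|---|---|---|---|
| Day 1 | intensive | sparse | 40 / 40 / 15 |
| Weeks 2, 4, 8 | sparse | sparse | 50 / 50 / 25 |
| Week 12 | intensive | sparse | 40 / 40 / 15 |

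The totals are 95 and 125. The share absent on Day 1 and Week 12 is 10/50 = 20% of each active arm and 10/25 = 40% of placebo. Ten is a minimum. An assumed 15 per arm gives 35/35/10, or 30% and 60% absent. Placebo matters for PD only, since SAP 8.8.1 limits PK to active arms.

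Protocol Table 19, footnote 16, does not exempt substudy subjects from sparse PD sampling on Day 1 and Week 12. However, SAP 8.8 gives each subject one schedule on those days, and Protocol 8.4.3 keeps population PK sampling for subjects outside the substudy.

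**2. Precision of the Week 12 PD contrast.** In SD units, SE = √(1/n_active + 1/n_placebo).

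- Sparse only: √(1/40 + 1/15) = 0.303.
- All subjects: √(1/50 + 1/25) = 0.245.
- Ratio: 0.303/0.245 = 1.24. With 15 per arm: √(1/35 + 1/10) = 0.359, ratio 1.46.

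These are whole-visit counts, with full attendance and one value per subject, whereas the model is fitted bin by bin. They fit only the predose timepoint and the 2.0 h bin, where nearly everyone is due a sample. The second sparse sample has no fixed time and scatters over the later bins.

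**3. Shift from the change in mix.** Let f be the substudy share and d the difference between substudy and other subjects. The all-subject mean exceeds the non-substudy mean by f × d.

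- Active: 0.20 × 0.2 = 0.04 SD, to 0.20 × 0.5 = 0.10 SD.
- Placebo: 0.40 × 0.2 = 0.08 SD, to 0.40 × 0.5 = 0.20 SD.

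**4. Which intensive samples can join the bins.** A 2 h sample within ±10 minutes falls at 1 h 50 to 2 h 10, inside the 2.0 h bin (1 to under 3 h). The 6 and 8 h samples also land inside their bins (5 to under 7 h, 7 to under 9 h). The difficulty there is composition. At Weeks 2, 4 and 8 a substudy subject gives two postdose samples, the first at 1 to 3 h, so at most one can fall in the 6.0 or 8.0 h bin. On Days 1 and 84 the same subject would fill both.

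**The case against.** Reporting the two schemes separately is a defensible choice, and several features limit the harm.

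- Each arm contrast within a visit uses one set of subjects, and no test between visits is planned.
- Day 1 and Week 12 have the same scheduled subjects within each scheme.
- The longitudinal predose PK plot is already pooled.
- Sparse PD is analysed as change from baseline with baseline as covariate, so a difference in level between volunteers and others largely cancels. A spurious step needs a difference in response.
- Sparse sampling times vary by subject and visit, so membership of the later bins already changes.

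All of this stands, and it rules out some stronger readings. A reader might infer that the visits compare different groups. They are nested: at the substudy minimum, 40/50 = 80% of each active arm and 15/25 = 60% of placebo are scheduled in the sparse set at all five visits. A reader might infer that data are lost, but they are reported in the intensive tables. A reader might apply the 1.24 to every postdose bin, which the bin-by-bin models do not support. Nor does any visible text say that the sparse by-visit tables decide dose or durability; most of the dose rationale is blacked out.

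The objection does not answer the Week 12 gap: at predose and around 2 h almost every subject is due a sample, and no planned PD model uses them together.

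**Conclusion.** The point holds as a minor one, worth making because it is cheap. No planned Week 12 ANCOVA of FGF19, C4 or bile acid covers the population that the SAP and protocol name for it. At predose and 2.0 h the standard error is about 1.24 times the pooled value with 10 substudy subjects per arm, and more if the substudy is larger. That rests on planned arm sizes and no dropout.

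The drift in by-visit means, 0.04 to 0.10 SD (active) and 0.08 to 0.20 SD (placebo, PD only), depends wholly on the assumed 0.2 to 0.5 SD difference. The documents neither support nor exclude that difference; entry to the substudy is by agreement, so some selection is possible. The primary ALT analysis in SAP 8.6.2 is unaffected.

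**What to change.** In SAP 8.8.1.1 and 8.8.2.1, bring two sets of Day 1 and Day 84 intensive samples into the by-visit summaries and, for PD, into the ANCOVA:

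- the predose samples, which extends to PD the pooling rule that SAP 8.8.1.2 already has for predose PK;
- the 2 h samples, placed in the 2.0 h bin by actual elapsed time.

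Keep the 6 and 8 h samples in the separate intensive profiles as planned. Do not use pooled 6.0 and 8.0 h bins for reading across visits. A reader might expect pooling all three times to give the same subjects in every bin at every visit. It would not: substudy subjects would fill both late bins on Days 1 and 84 only, which recreates the problem, and they have no scheduled 4 h sample on those days.

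The cost is a sentence in each section and a small programming change, with no new samples. The 2.0 h bin would mix fixed-time and free-time samples, which binning by actual time already handles.

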8.8.1 Pharmacokinetic (PK) Analysis

The PK analysis will use the pharmacokinetic population and will include only subjects in active treatment arms.

8.8.1.1 Analysis of Sparse PK Samples

The concentration data for EDP-305 and each metabolite collected according to the sparse sampling scheme will be summarized by active treatment arm, visit, and bin time midpoint. Concentrations that are below the limit of quantitation (BLQ) will be treated as zero for the computation of descriptive statistics. If more than 50% of subjects have postdose concentration values below BLQ, descriptive statistics will not be presented except for maximum and BLQ will be displayed for mean and minimum. The number of observations, arithmetic mean, standard deviation (SD), % coefficient of variation (%CV), median, minimum, maximum, geometric mean, and %CV of the geometric mean (%GCV) will be displayed. Linear and semi-log plots of the arithmetic mean concentration versus bin time will be created. The linear plots of mean concentrations will include the SD (\pm) for each mean. Composite (i.e. “spaghetti”) plots of individual subject EDP-305 and metabolite plasma concentrations versus time data will be created on both the linear and semi-logarithmic scales. A summary plot of the means and SD of the pre-dose concentrations at each visit will be provided by treatment.

Individual data will be presented in listing.

8.8.1.2 Analysis of Intensive PK samples

The concentration data for EDP-305 and each metabolite collected according to the intensive sampling scheme will be summarized by active treatment arm, visit and nominal time since the reference dose. Concentrations that are BLQ will be treated as zero for the computation of descriptive statistics. If more than 50% of subjects have postdose concentration values below BLQ, descriptive statistics will not be presented except for maximum and BLQ will be displayed for mean and minimum. The number of observations, arithmetic mean, SD, %CV, median, minimum, maximum, geometric mean, and %GCV values will be displayed. Linear and semi-log plots of the arithmetic mean concentration versus nominal sampling time will be created. The linear plots of mean

concentrations will include the SD (\pm) for each mean. Composite (i.e. “spaghetti”) plots of individual subject EDP-305 and metabolite plasma concentrations versus time will be created on both the linear and semi-logarithmic scales. Predose samples collected under to the intensive sampling scheme will be pooled with those collected under the sparse sampling scheme for the purpose of creating the longitudinal summary plot of the means and standard deviations of the pre-dose concentrations (See Section 8.8.1.1). Linear and semi-logarithmic plots of the individual plasma concentration by actual sampling time will be provided by subject (one subject per page, Day 1 and Day 84 on same plot).

The PK parameters listed in Table 6 will be calculated as indicated for plasma EDP-305 and its metabolites, as applicable. PK parameters will be calculated by noncompartmental methods (only on Day 1 and Day 84).

Table 6: PK/PD Parameters for Subjects with Intensive Samples

PK Parameter	Description
AUC_{last}	The area under the plasma concentration-time curve from time zero to the time of the last quantifiable concentration computed using the linear up/log down trapezoidal rule.
C_{max}	Maximum observed concentration.
T_{last}	Time to last quantifiable concentration.
T_{max}	Time to reach C_{max} . If the maximum value occurs at more than one timepoint, T_{max} is defined as the first time point with this value.

Plasma PK parameters for each dose level will be calculated from the concentrations of EDP-305 and its metabolites measured in predose and post-dose plasma samples. For each EDP-305 dose level, descriptive statistics of AUC_{last} and C_{max} (sample size, arithmetic means, geometric means, standard deviation (SD), %CV, minimum, median, maximum, and %GCV) will be presented. Only the minimum, median, and maximum will be presented for T_{max} . T_{last} will be presented as a diagnostic parameter in the listing of individual PK parameters, but will not be included in summary tables with other PK parameters.

Individual data will be presented in listing.

8.8.2 Pharmacodynamic (PD) Analysis

The PD analysis will use the efficacy population and will include all treatment arms (active and placebo).

8.8.2.1 Analysis of Sparse PD Samples

A descriptive summary will be provided for the FGF19, C4, and bile acid endpoints including measured concentrations, change from baseline, and percentage change from baseline using the 8-number summary by visit, treatment group, and bin time midpoint.

Change from baseline and percentage change from baseline in the FGF19, C4, and bile acid concentrations for each bin time midpoint by visit will be analysed using an ANCOVA model with treatment as fixed effect and the associated baseline value as covariate with the Week 12 visit being considered the primary visit of interest. Least squares means and standard errors will be presented for each visit, p-value and 2-sided 95% confidence interval for treatment differences will be presented for each visit. Significance tests will be based on least-squares means using a two-sided $\alpha = 0.05$.

A by-subject listing will be provided for observed and derived variables.

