4.2 Secondary efficacy endpoint(s)

The secondary efficacy endpoints are as follows:

- Change from Baseline in percentage of fat in the liver as assessed by MRI-PDFF at Week 12
- Change from Baseline in liver stiffness as assessed by magnetic resonance elastography (MRE) at Week 12
- Change from Baseline of noninvasive liver fibrosis markers (ELF panel) and PRO C3 at Week 12
- Change from Baseline in NFS, APRI, and FIB-4 at Week 12
- Change from Baseline in TG, TC, HDL-C, LDL-C, adiponectin, and ApoA1, B, C3 at Week 12
- Change from Baseline in fasting glucose and insulin, HOMA index (in nondiabetic subjects) and HbA1c in subjects with T2DM at Week 12
- Change from Baseline in fibrinogen, CRP, IL6, IL1 β , TNF- α , TNF- β , alpha2 macroglobulin and haptoglobin levels at Week 12
- Pharmacokinetic parameters of EDP-305 (and metabolites): C_{max} , T_{max} , and AUC_{last}
- Change from Baseline in body weight at Week 12
- Change in waist to hip WTH ratio at Week 12
- Pharmacodynamic parameters of EDP-305: FGF19, C4, and bile acid (BA) at Week 12

In addition, the percentage change from Baseline in the primary endpoint and all secondary endpoints will be summarized (as applicable).

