8.8.2.2 Analysis of Intensive PD Samples

A descriptive summary will be provided for the FGF19, C4, and bile acid endpoints including measured concentrations, change from baseline, and percentage change from baseline using 8-number summary by visit, treatment group, and nominal time. For Days 1 and 84 (overlaid), linear plots of the arithmetic mean concentration (\pm SD) versus nominal sampling time figures will be created for FGF19, C4, and bile acid endpoints.

Change from baseline and the percentage change from baseline in the FGF19, C4, and bile acid concentrations for each nominal time by visit will be analysed using an ANCOVA model with treatment as fixed effect and the associated baseline value as covariate with the Week 12 visit being considered the primary visit of interest. Least squares means and standard errors will be presented for each visit, p-value and 2-sided 95% confidence interval for treatment differences will be presented for each visit. Significance tests will be based on least-squares means using a two-sided $\alpha = 0.05$.

The area under the curve from 0 to 8 hours (AUC_{0-8}) and from 2 to 8 hours (AUC_{2-8}) will be computed for FGF19 and C4 at Days 1 and 84 using the linear trapezoidal rule.

Descriptive summaries of AUC_{0-8} and AUC_{2-8} (sample size, arithmetic means, geometric means, standard deviation (SD), %CV, minimum, median, maximum, and %GCV) for FGF19 and C4 will be presented by visit and treatment group.

The change from baseline and percent change from baseline for AUC_{0-8} and AUC_{2-8} will be computed for Day 84 using the parameter value at Day 1 as the baseline value.

Change from baseline and the percentage change from baseline in the AUC_{0-8} and the AUC_{2-8} for FGF19 and C4 at Day 84 will be analysed using an ANCOVA model with treatment as fixed effect and the associated baseline value as covariate. Least squares means and standard errors will be presented for each visit, p-value and 2-sided 95% confidence interval for treatment differences will be presented for each visit. Significance tests will be based on least-squares means using a two-sided $\alpha = 0.05$.

A by-subject listing will be provided for observed and derived variables. Composite (i.e.

“spaghetti”) plots of individual subject FGF19, C4, and bile acid concentrations versus time will be created on the linear scale.

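### Week 12 FGF19, C4 and bile acid: the fasting predose sample common to both sampling schemes has no pooled treatment comparison in SAP 8.8.2

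*SAP*

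**What the plan says.** - **Endpoint.** SAP 4.2 lists as a secondary efficacy endpoint "Pharmacodynamic parameters of EDP-305: FGF19, C4, and bile acid (BA) at Week 12". Protocol 11.6.1 includes the same item in a list to be compared by ANCOVA in the efficacy population.
- **Population.** SAP 8.6.3 and 8.8.2 both name the efficacy population for PD, and 8.8.2 includes all arms.
- **Sampling.** Under SAP 8.8, substudy subjects are sampled at predose, 2, 6 and 8 h on Days 1 and 84, and all other subjects at predose and twice after the dose. Footnotes 16 and 17 of the SAP schedule of assessments ask for at least an 8-hour fast in both schemes. At Weeks 2, 4 and 8 everyone follows the sparse scheme.
- **Models.** SAP 8.8.2.1 fits an ANCOVA to sparse samples "for each bin time midpoint by visit". SAP 8.8.2.2 fits a separate one to intensive samples, on "concentrations for each nominal time by visit". The ANCOVAs of the area under the curve cover intensive subjects only, and only FGF19 and C4.
- **Predose handling.** The bin table in SAP 8.8 begins at a 0.5 h midpoint. The text after it assigns sparse predose samples to a 0-hour bin for use in plots. For drug concentrations, SAP 8.8.1.2 states that "Predose samples collected under to the intensive sampling scheme will be pooled with those collected under the sparse sampling scheme", for a longitudinal plot. SAP 8.8.2.4 uses Week 12 predose PD values from all subjects, in scatterplots.
- **Substudy size.** SAP 3.2.1: "A minimum of 10 subjects per treatment group will be included in the PK/PD substudy". No maximum or target is given.

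**The concern.** These markers are the trial's direct evidence of FXR engagement. The one measurement taken in the same way from every subject at Week 12 is the fasting predose value. An analyst who follows 8.8.2.1 and 8.8.2.2 literally would not produce a treatment comparison of it in the named population. There would be one result from intensive subjects, and either a second from sparse subjects or none, depending on how the 0-hour bin is read.

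Two things are at stake. The reader gets no single result that answers the secondary endpoint, and each result that is produced is less precise than the data allow. Placebo, the smallest arm, is thinned most: 10 substudy subjects are 10/25 = 40% of placebo but 10/50 = 20% of each dose group.

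**Working it through.** **Is a pooled test specified anywhere?** Week 12 predose PD values appear in four places in the SAP:

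- 8.8.2.1: ANCOVA, sparse subjects only, and only if the 0-hour plotting bin counts as a bin for analysis.
- 8.8.2.2: ANCOVA, intensive subjects only (predose is one of the nominal times).
- 8.8.2.3: scatterplots for intensive subjects.
- 8.8.2.4: scatterplots for all subjects, with no treatment comparison.

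None is an efficacy-population treatment comparison. SAP section 9 lists no departure from protocol 11.6.1 on this point.

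**Plan's own figure.** The documents give no power or precision figure for PD. Their only one is for ALT: 44 versus 22, difference 30, SD 40, two-sided 0.05, stated power 80.438%. A noncentral t calculation with 64 degrees of freedom and a standardised difference of 30/40 = 0.75 gives 80.76%, which agrees closely. The same method is used below.

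**Inputs.** Randomised numbers are 50 per dose group and 25 placebo (SAP 3.2.1). The substudy size is an assumption: 10 per arm (the stated minimum), 15 per arm, or 20/20/10 (in proportion to the 2:2:1 allocation).

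**Formula.** SE of dose minus placebo, in SD units, is √(1/n_dose + 1/n_placebo). The baseline covariate is ignored, since it would scale all SEs about equally.

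- Pooled: √(1/50 + 1/25) = √0.0600 = 0.245
- Sparse, 10 per arm removed: √(1/40 + 1/15) = √0.0917 = 0.303
- Intensive, 10 per arm: √(1/10 + 1/10) = √0.2000 = 0.447

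| Substudy | Analysis | n, dose vs placebo | SE (SD units) | Ratio to pooled | Detectable at 80% power (SD units) |
|---|---|---|---|---|---|
| any | pooled predose | 50 vs 25 | 0.245 | 1.00 | 0.70 |
| 10/10/10 | sparse | 40 vs 15 | 0.303 | 1.24 | 0.86 |
| 10/10/10 | intensive | 10 vs 10 | 0.447 | 1.83 | 1.33 |
| 15/15/15 | sparse | 35 vs 10 | 0.359 | 1.46 | 1.03 |
| 15/15/15 | intensive | 15 vs 15 | 0.365 | 1.49 | 1.06 |
| 20/20/10 | sparse | 30 vs 15 | 0.316 | 1.29 | 0.91 |
| 20/20/10 | intensive | 20 vs 10 | 0.387 | 1.58 | 1.12 |

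The sparse rows assume that predose is tested as a bin. The ratios are of SEs. Confidence-interval ratios are a little larger because degrees of freedom fall: with 10 per arm the half-widths are 0.488, 0.607 and 0.940 SD, so 0.607/0.488 = 1.24 and 0.940/0.488 = 1.93.

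**Completers.** With 44 versus 22 in total, and all substudy subjects completing, the pooled SE is 0.261. At 10 per arm the sparse (34 vs 12) and intensive ratios are 1.29 and 1.71. At 15 per arm they are 1.61 (29 vs 7) and 1.40.

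**Recovery by combination.** Weighting the two scheme-specific estimates by inverse variance (10 per arm, randomised) gives SE = √(1/(1/0.0917 + 1/0.2000)) = 0.251, against 0.245 pooled. That is about 2% larger. No such combination is planned.

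**The case against.** The best defence is that an all-subject comparison is plainly intended. Protocol 11.6.1 calls for an ANCOVA in the efficacy population, SAP 8.6 makes that population primary for all efficacy analyses, SAP 8.6.1 gives a general Week 12 ANCOVA for change from baseline, and 8.8.2 repeats the population. That stands as a statement of intent, so a reader who infers that the plan rejects an all-subject comparison goes too far. But naming a population does not specify a model. The PD endpoint is not worded as a change from baseline, so 8.6.1 does not clearly reach it, and the specific sections each restrict the ANCOVA to one scheme's samples.

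A reader might also infer that the evidence of target engagement is split throughout the trial. It is not: at Weeks 2, 4 and 8 all subjects follow the sparse scheme, and only the unclear status of the predose bin carries over to those visits.

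Nor is information lost. All samples are collected and listed, and combining the two schemes would recover nearly all the precision. The 1.83 ratio describes a substudy that is small by design and should not be read alone. Separate post-dose analyses are reasonable because sampling times differ. Finally, these are unadjusted secondary PD tests in a Phase 2 trial, the documents give no PD effect size or SD, and the primary endpoint is untouched. All of this limits the weight of the point without removing it.

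**Conclusion.** The point holds as a gap between the stated population and the specified models. It is confined to the shared fasting predose value, and the split to Days 1 and 84. As written, the SAP yields two smaller Week 12 predose tests, or one small intensive test and no clear sparse one.

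Using randomised numbers and equal variances, the SE penalty relative to pooling is 24% (sparse) and 83% (intensive) at exactly 10 per arm, and 46% and 49% at 15 per arm. The size depends on the actual substudy numbers, which the documents do not give; the direction does not. The documents do not support a claim that any conclusion would change. They do support saying that the endpoint lacks one named, full-population result that its data could readily provide.

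**What to change.** Add to SAP 8.8.2 one ANCOVA for each of FGF19, C4 and bile acid on the Week 12 predose value, expressed as change from the Day 1 predose value, with treatment and that Day 1 baseline in the model. Pool both schemes over the efficacy population and name this as the analysis of the PD secondary endpoint. Say explicitly whether the 0-hour bin is an analysis bin or only a plotting device. Keep the bin and nominal-time analyses as supportive.

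If substudy subjects make up different shares of the arms (as at 10/10/10), a sensitivity analysis with scheme as a factor would guard against a difference between the two sets of subjects. By the combination result above, its SE would be about 0.251 rather than 0.245 SD.

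The cost is one extra table per marker and no new data. The change can go through the SAP change log before database lock, as SAP section 1 provides.
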